## 5.5. Prophylactic and Standard of Care Migraine Medications

Participants using prophylactic migraine medications are permitted to remain on therapy if the dose has been stable for at least 2 months prior to the Baseline Visit and this dose is not expected to change during the study. Participants who previously discontinued prophylactic migraine medication must have done so at least 5 half-lives of the prophylactic medication prior to the Screening Visit.

Participants may need to take previously prescribed standard of care medications: aspirin, ibuprofen, acetaminophen (including Excedrin®Migraine) up to 1000 mg/day for a maximum of 2 consecutive days at a time, naproxen (or any other type of non-steroidal anti-inflammatory [NSAID]), antiemetics (eg, metoclopramide or promethazine), or muscle relaxants, which are used during the study (Observation Period and Long-Term Treatment Phase) for the standard of care treatment of migraine.

Use of triptans by participants without a contraindication to their use is allowed during the Observation Phase but must be discontinued at the Baseline Visit. As described above, use of triptans is prohibited during the Long-Term Treatment Phase. With the exception of triptans described in this section, participants are allowed to take standard treatment for migraine during the study, if needed, but are required to meet dose restrictions if taking acetaminophen (no more than 1000 mg/day at a time for 2 consecutive days).

If a participant takes a tablet of study drug and experiences a migraine later that day, the participant can take standard of care medications for migraine (as described in this section above) after taking the study drug that day. Participants are not allowed to take more than 1 tablet of the study medication per calendar day.

Use of standard of care medications during Observation Period and Long-Term Treatment Phase, will be recorded by the participant via BYOD and reported to the site.

## **5.6. Contraception**

The investigator or their designee, in consultation with the participant, will confirm that the participant is utilizing an appropriate method of contraception for the individual participant from the permitted list of contraception methods (see Section 12.3.4) and will confirm that the participant has been instructed in its consistent and correct use.

The investigator or designee will inform the participant of the need to use acceptable effective contraception consistently and correctly and document the conversation and the participant's affirmation in the participant's chart. Participants need to affirm their consistent and correct use of at least 1 of the selected methods of contraception, considering that their risk for pregnancy may have changed since the last visit.

The investigator or designee will inform the participant of the need to use acceptable effective contraception consistently and correctly and document the conversation and the participant's affirmation in the participant's chart. Participants need to affirm their consistent and correct use of at least 1 of the selected methods of contraception, considering that their risk for pregnancy may have changed since the last visit.

WOCBP will complete a pregnancy test at the Screening Visit, at the Baseline Visit, at Weeks 4, 8, and at all on-site study visits through the Week 52/end of treatment visit and at the Safety follow up Visit. If a WOCBP suspects that she might be pregnant, she should not take the study drug and should contact the study doctor immediately.

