A multicenter open-label, long-term study (BHV3000-201) was conducted to evaluate the safety and tolerability of rimegepant 75 mg tablet taken as needed (up to 1 tablet per day upon onset of a migraine of mild, moderate, or severe intensity) for the acute treatment of migraine for up to 52 weeks. This multiple-dose, long-term study of rimegepant 75 mg administered for up to 52 weeks confirmed the favorable safety profile across a variety of safety endpoints, including AE assessments, clinical laboratory testing including LFTs, vital signs and ECGs. Safety data from the double-blind treatment and the open-label extension phases of the pivotal Phase 2/3, randomized, double-blind, placebo-controlled preventive treatment of migraine study (BHV3000-305) support a favorable safety profile of rimegepant 75 mg administered EOD for the preventive treatment of migraine. Rimegepant 75 mg administered EOD + PRN for up to 52 weeks in the open-label phase is well tolerated, with no new safety signals observed in the open-label-extension phase. It is not known if it is safe to take more than 18 doses of rimegepant in 30 days. Taking into account the measures to minimize risk to participants with episodic migraine, the potential risks associated with rimegepant are justified by the anticipated benefits that may be afforded to participants with daily dosing regimens.

There are no adequate data on the developmental risk associated with the use of rimegepant in pregnant women. Women of childbearing potential (WOCBP) must have a negative pregnancy test and WOCBP must use an acceptable method of contraception to avoid pregnancy throughout the study in such a manner that the risk of pregnancy is minimized. Participants undergo regular pregnancy testing throughout the duration of the study. Although no safety issues in clinical trials of rimegepant were observed, cardiovascular events, cerebrovascular events, hypertensive events, and serious gastrointestinal events associated with constipation are reviewed in each aggregate report per FDA request. None of these reviews have detected any safety signal associated with these events. Participants are excluded if there is uncontrolled, unstable, or recently diagnosed cardiovascular disease or hypertension. Participants are monitored through multiple safety endpoints, including AE assessments, clinical laboratory testing, vital signs and ECGs.

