**Table 1. Assessment Schedule**

Procedure	Screening Visit	Observational Period (30 days, ±2 days)	Baseline Visit (Day 1)	Phone visit to confirm eligibility based on Clinical Laboratory Findings	Weeks 4, 8, 12 (all visits ±3 days)	Weeks 16, 28, 40, 52 (or Early Termination) (all visits ±7 days)	Phone visits Weeks 20, 24, 32, 36, 44, 48(all visits ±7 days)	Follow-up Safety Visit (14 days after EOT visit ±2 days)
Clinical Safety Laboratory Testing	X		X		X	X		X
Lipid Panel			X			X (Weeks 28 and 52/early termination only)		
ECG	X		X			X (Weeks 28 and 52/early termination only)		X
Urinalysis	X		X			X (Week 52/early termination only)		
Urine Drug Screen for drugs of abuse	X							
FSH, if applicable, to determine WOCBP status 	X							
Pregnancy Test 	X (urine)		X (urine and serum)		X(urine)	X (urine)	X (urine)	X (urine)
AE and SAE assessment 	X	X	X		X	X	X	X
Clinical Drug Supplies/Study Supplies								
Dispense Study Medication 			X		X	X		

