**Table 1. Assessment Schedule**

Procedure	Screening Visit	Observational Period (30 days, ±2 days)	Baseline Visit (Day 1)	Phone visit to confirm eligibility based on Clinical Laboratory Findings	Weeks 4, 8, 12 (all visits ±3 days)	Weeks 16, 28, 40, 52 (or Early Termination) (all visits ±7 days)	Phone visits Weeks 20, 24, 32, 36, 44, 48(all visits ±7 days)	Follow-up Safety Visit (14 days after EOT visit ±2 days)
------------------	------------------------	--	---	---	--	---	--	---

6. Upon completion of the Baseline Visit, WOCBP will be provided with urinary pregnancy test kits so that participants can test at home if necessary. When WOCBP participants cannot confirm pregnancy status, a urine pregnancy test must be completed at home before taking study drugs.
7. All SAEs and AEs must be reported by the participant after signing the informed consent.
8. To be determined to be eligible prior to dispensing study drug, participants must have a history of migraine attacks for at least 6 days during the 30-day Observation Period and WOCBP must have a negative pregnancy test result prior to dispensing study drug. Week 4, 8, 2: dispensing 3 wallets to the participant on the monthly visits. Week 16, 28, 40: according to the participant's need to dispense wallets, maximum is 7 wallets. The study drug will not dispense at Week 52 as that is EOT.
9. Participants will be instructed that they can take the study medication at the time of their migraine attack (mild, moderate, or severe), up to 1 tablet per day. The participant must record in the BYOD the study drug taken for each tablet.
10. If a participant lacks 6 or more eDiary reports per month for 2 months (continuous or non-continuous), the participant's continued participation in the study should be terminated due to lack of compliance.
11. The eDiary will be dispensed at the Screening Visit after the participant has completed all screening procedures. Participants will be trained in the use of the eDiary. Participants will use eDiary daily during the observation and Long-Term Treatment Periods to record migraine attacks, migraine severity, and whether they receive migraine treatment.

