#### **4.3.2. Long-term Treatment Period (52 weeks)**

After completing the 30-day Observation Period, the participants will return to the clinical site for the Baseline Visit (Day 1). The main operations or examinations to be completed by the participants included:

- Evaluation of inclusion/exclusion criteria;
- Recording prophylactic and standard of care migraine medications/concomitant medications via BYOD;
- Physical examination;
- Vital signs/physical measurements;
- Clinical safety laboratory tests;
- Lipid panel
- ECG;
- Urine routine;
- Pregnancy test (urine and serum);
- AE and SAE assessments;
- Dispense study drug;
- Return eDiary and review eDiary and BYOD of completion for completeness;
- Daily recording of migraine attacks and their severity by eDiary;

- MSQoLQ version 2.1;
- MIDAS.

After the completion of the relevant items at the Baseline Visit (Day 1), before the participants take the study drug for the first time, the clinical site staff should confirm the eligibility of the participants for participating in the study based on the examination results at the Baseline Visit, and inform the participants by telephone of the eligibility results. The participants who meet all the inclusion criteria and do not meet the exclusion criteria can participate in the trial. Participants confirmed to be eligible by a telephone visit may start taking the study drug, rimegepant 75 mg (up to 1 tablet per day) at the time of a migraine attack (mild, moderate, or severe) and record the use of the study drug with BYOD.

Participants will make site visits at Weeks 4, 8, 12 ( $\pm 3$  days) and Weeks 16, 28, 40, 52 ( $\pm 3$  days) or Early Termination of the trial and telephone visits at Weeks 20, 24, 32, 36, 44, 48 for the Long-Term Treatment Period as follows:

- Recording prophylactic and standard of care migraine medications/concomitant medications via BYOD;
- Physical examination (Weeks 28 and 52 or early termination);
- Vital signs/physical measurements (at each site visit);
- Clinical safety laboratory tests (at each site visit);
- Lipid panel (at Weeks 28 and 52 or early termination);
- Electrocardiogram (at Weeks 28 and 52 or early termination);
- Urine routine (Week 52 or early termination);
- Urine pregnancy (at each site visit and at each telephone visit);
- AE and SAE assessments (at each site visit and at the telephone visit);
- Dispense study drug (at each site visit);
- Take the study drug;
- Record the use of study medication via BYOD;

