#### **6.1.4.2. Pregnancy Test**

WOCBP will perform pregnancy testing at the Screening Visit, at the Baseline Visit, at scheduled site visits (Weeks 4, 8, 12, 16, 28, 40, 52, or early termination), and at the Safety follow up Visit as specified in [Table 1](#), along with serum and urine pregnancy tests at the Baseline Visit and urine pregnancy tests at other times. Upon completion of the Baseline Visit, when WOCBP participants cannot confirm pregnancy status, a urine pregnancy test must be completed at home before taking study drugs.

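### Protocol 5.6 and 6.1.4.2 leave out the six phone-visit pregnancy tests that Table 1 and 4.3.2 require; a site working from 5.6 would test every 12 weeks after Week 16 instead of every 4

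*Protocol*

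**What the plan says.** Four places in the protocol set out when pregnancy tests are done.

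- **Table 1 (Schedule of Activities).** The Pregnancy Test row is marked for a urine test in the column headed "Phone visits Weeks 20, 24, 32, 36, 44, 48", as well as in every on-site column.
- **Section 4.3.2.** The treatment-period procedures include "Urine pregnancy (at each site visit and at each telephone visit").
- **Section 5.6 (Contraception).** After Screening and Baseline, tests fall "at Weeks 4, 8, and at all on-site study visits through the Week 52/end of treatment visit", and then at the safety follow-up visit. Phone visits are not named and Table 1 is not cited.
- **Section 6.1.4.2 (Pregnancy Test).** After Screening and Baseline, tests fall "at scheduled site visits (Weeks 4, 8, 12, 16, 28, 40, 52, or early termination), and at the Safety follow up Visit". The same sentence then refers to Table 1. The pointer leads to the full schedule, but the weeks listed are the site visits only.

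Two other statements bear on this. Section 2.5 says "There are no adequate data on the developmental risk associated with the use of rimegepant in pregnant women" and names regular testing during the study as a protection. Table 1, footnote 6, gives a conditional rule: "When WOCBP participants cannot confirm pregnancy status, a urine pregnancy test must be completed at home before taking study drugs".

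**The concern.** All four places agree up to Week 16, because every visit until then is on site. After that, site visits are 12 weeks apart and the intervening 4-weekly contacts are by phone. Whether the phone visits carry a test therefore decides whether testing is 4-weekly or 12-weekly for the rest of the year.

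Section 5.6 is where a site would look for its contraception and pregnancy duties. Its list reads as complete and leads nowhere else. A site working from it would do one of every three tests required after Week 16.

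At stake is how long an unrecognised pregnancy could go on with drug exposure. At Weeks 16, 28 and 40 participants can be given up to seven wallets, so they hold study drug at home through the intervals that 5.6 leaves untested. Section 8.11.1 requires permanent discontinuation once pregnancy is found, and reporting within 24 hours of awareness. A later test delays both.

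There is also a smaller record-keeping effect. SAP Appendix 8.2 maps a missing pregnancy test from the old Major deviations to an Important category, and SAP 7.3.2 summarises Important deviations. With two lists in one protocol, the same missed Week 20 test could be called a deviation at one site and not at another.

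**Working it through.** **Inputs**

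- Site visits on treatment: Weeks 4, 8, 12, 16, 28, 40, 52 (Table 1; 6.1.4.2). That is 7 visits.
- Phone visits: Weeks 20, 24, 32, 36, 44, 48 (Table 1). That is 6 visits.
- Visit windows: Table 1 gives ±7 days for the site visits from Week 16 onward, and for the phone visits ("Phone visits Weeks 20, 24, 32, 36, 44, 48(all visits ±7 days"). Section 4.3.2 gives ±3 days for the site visits at Weeks 16, 28, 40 and 52.

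**Step 1: the plan's own interval.** Section 4.1 says site visits are 12 weeks apart after Week 16. From the visit weeks, 28 − 16 = 12, 40 − 28 = 12 and 52 − 40 = 12. The figure is reproduced.

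**Step 2: number of on-treatment tests after Baseline.**

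| | Table 1 and 4.3.2 | 5.6 as listed |
|---|---|---|
| Baseline to Week 52 | 7 + 6 = 13 | 7 |
| After Week 16 | 3 + 6 = 9 | 3 (Weeks 28, 40, 52) |

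The share omitted after Week 16 is 6/9, or two in three.

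**Step 3: nominal gaps between consecutive tests.**

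- Table 1 and 4.3.2: thirteen gaps of 4 weeks each, or 4 × 7 = 28 days.
- Section 5.6: four gaps of 4 weeks up to Week 16, then three gaps of 12 weeks (16–28, 28–40, 40–52), or 12 × 7 = 84 days each.

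**Step 4: longest gap after Week 16 that the windows allow.** The formula is the nominal gap plus the late allowance at the second visit plus the early allowance at the first.

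- Table 1 windows, site and phone tests: 28 + 7 + 7 = 42 days.
- Table 1 windows, site tests only: 84 + 7 + 7 = 98 days.
- Site windows of ±3 days from 4.3.2, site tests only: 84 + 3 + 3 = 90 days. The 42-day figure does not change, because it still applies between two consecutive phone visits such as Weeks 20 and 24.

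The choice of window moves only the worst case under 5.6 (90 or 98 days). The 84-day nominal gap and the six omitted tests are the same either way.

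**The case against.** The strongest reply is that the operative schedule is not in doubt. Section 4.1 sends the reader to Section 4.3 for assessments and visits, and Table 1 and 4.3.2 agree there. Section 6.1.4.2 brings Table 1 in by reference. Neither 5.6 nor 6.1.4.2 says that tests are confined to site visits, so a site that follows Table 1 complies with all four places. The 12-week gap arises only if a site relies on 5.6 alone. This stands, and it is why the consequence is stated for a site working from 5.6 and not for every site. It does not make the two lists correct.

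The second reply is that other protections exist. Women receive home test kits after Baseline and must test before dosing if they cannot confirm their status. Section 5.6 tells them not to dose if they suspect pregnancy and asks them to affirm correct contraceptive use. Adverse events are assessed at each phone visit, so contact remains 4-weekly. The home-test rule can even be read as requiring positive confirmation before dosing. These are real safeguards. On the more natural reading, however, the home-test rule and the no-dosing rule are triggered by uncertainty or suspicion. Contraceptive affirmation and phone contact do not detect pregnancy. Only a scheduled test reliably covers a pregnancy that nobody suspects.

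The third reply is that the SAP already has a deviation category for a missing pregnancy test. It does, but the category does not say which list decides whether a test was due.

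**Conclusion.** The inconsistency is real and lies within the current protocol text. Followed as written, 5.6 drops 6 of the 13 on-treatment tests after Baseline, all of them after Week 16, and lengthens the nominal gap from 28 to 84 days. With Table 1's windows the longest gap is 98 days instead of 42.

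The conclusion takes Table 1 and 4.3.2 as the governing schedule. They agree with each other, and the protocol's summary of changes gives monthly testing as the aim. That last point is context only; the conflict does not depend on it.

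The documents do not show how sites actually scheduled tests, or how many women of childbearing potential were still on treatment when Version 5.0 took effect. The number of tests actually missed is therefore unknown. No endpoint, sample size, power or interval estimate is affected; the only summary touched is that of protocol deviations. The correction should be made because the instruction concerns participant safety and costs almost nothing to put right.

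**What to change.** Keep the 4-weekly schedule. In Sections 5.6 and 6.1.4.2, either add the phone visits at Weeks 20, 24, 32, 36, 44 and 48, or replace both lists with one sentence requiring a test at every site and phone visit shown in Table 1. If no amendment is planned, a clarification letter to sites would do.

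State also that a missing phone-visit test is judged against Table 1, from the date Version 5.0 takes effect, so that all sites classify it alike.

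The cost is a few words in two sections. There is no statistical cost, and no test is added beyond those Table 1 already requires.

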## **6. STUDY CONDUCT AND DESCRIPTION OF STUDY PROCEDURES**

### **6.1. Safety Assessments**

#### **6.1.1. Vital Signs and Physical Measurements**

Vital signs mainly include blood pressure, pulse rate, respiratory rate and body temperature. Vital signs will be measured at the Screening Visit, at the Baseline Visit, at scheduled site visits (Weeks 4, 8, 12, 16, 28, 40, 52, or early termination), and at the Safety follow up Visit as specified in [Table 1](#).

Physical measurements mainly include height and weight, and height is only measured at the Screening Visit. Weight measurement time and vital signs should be performed according to the schedule in [Table 1](#).

#### **6.1.2. Physical Examination**

Physical examination mainly includes skin, lymph nodes, eyes, head and neck, chest, abdomen, spine and limbs. Physical examinations will be performed at the Screening Visit, Baseline Visit, scheduled site visits (Week 28, Week 52, or early termination), etc. as specified in [Table 1](#).

The number of physical examinations may be increased if deemed necessary by the principal investigator.

#### **6.1.3. Electrocardiogram (ECG)**

A standard 12-lead ECGs will be performed at the Screening Visit, Baseline Visit, scheduled site visits (Week 28, 52, or early termination), and Safety follow up Visit as specified in [Table 1](#).

ECG examination indicators mainly include heart rate, PR interval, QRS duration, QT interval and QTc interval.

#### **6.1.4. Clinical Laboratory Tests**

##### **6.1.4.1. Safety Laboratory Testing**

Blood and urine samples for clinical laboratory assessments will be collected as outlined in [Table 1](#). A central laboratory vendor will be utilized for this study and a laboratory manual will be provided to each site. If possible, participants should be fasting for a minimum of 8 hours before each blood draw. However, if the participant is not fasting at the specified visit, the participant should still have blood drawn and the non-fasting status should be documented.

###### **1. Clinical Safety Laboratory Tests:**

Hematology: hemoglobin, hematocrit, red blood cell count, white blood cell count with differential count, and platelets;

Chemistry: Sodium, potassium, chloride, bicarbonate, calcium; glucose, HbA1c, BUN (urea), serum creatinine, uric acid, lactate dehydrogenase (LDH), total protein, albumin, creatine phosphokinase (CPK) (with fractionation test, if CK result is  $>1.5 \times$  ULN), eGFR using the estimated MDRD formula (calculated at central lab), AST, ALT, ALP and bilirubin (Total, Direct, Indirect);

2. Blood lipid test: cholesterol, low-density lipoprotein, high-density lipoprotein, triglyceride;
3. Urinalysis: pH, specific gravity, ketones, nitrite, urobilinogen, leukocyte esterase, protein, glucose and occult blood. Microscopic examination will be performed if occult blood, protein or white blood cells are positive;
4. FSH: for WOCBP at Screening Visit to determine WOCBP status;

Clinical safety laboratory tests will be performed at the Screening Visit, at the Baseline Visit, at scheduled site visits (Weeks 4, 8, 12, 16, 28, 40, 52, or early termination), and at the Safety follow up Visit as specified in Table 1; lipid panel tests will be performed at the Baseline Visit, at scheduled site visits (Weeks 28, 52, or early termination); urinalysis will be performed at the Screening Visit, at the Baseline Visit, and at scheduled site visits (Week 52 or early termination); and FSH is used by the study to determine WOCBP status at the Screening Visit as appropriate.

#### **6.1.4.2. Pregnancy Test**

WOCBP will perform pregnancy testing at the Screening Visit, at the Baseline Visit, at scheduled site visits (Weeks 4, 8, 12, 16, 28, 40, 52, or early termination), and at the Safety follow up Visit as specified in [Table 1](#), along with serum and urine pregnancy tests at the Baseline Visit and urine pregnancy tests at other times. Upon completion of the Baseline Visit, when WOCBP participants cannot confirm pregnancy status, a urine pregnancy test must be completed at home before taking study drugs.

